### 7.3.3 Biomarkers

Biomarker endpoints include the following:

- Kidney function markers (e.g., urine and serum creatinine, BUN/urea clearance, sodium, proteinuria, fractional excretion of sodium, urea, and urine output).
- Tubular injury biomarkers (e.g., KIM-1, IL 18, GST-alpha).
- Biomarkers for systemic inflammation (e.g., IL-6, CRP, LBP).
- Pharmacokinetics of recAP in all 3 active treatment groups in the first 120 patients from Part 1 only
- In addition to recAP PK concentration measurements, baseline (pre-dose) AP will be measured by activity (central laboratory)

### 7.3.4 Other Endpoints

Additional endpoints include the following:

- Composite endpoints – patients that meet, or do not meet, at least one of the following criteria:
  - a. Received RRT or died (prior to Day 28 [inclusive])
  - b. eGFR < 60 mL/min (at Day 60, estimated by a commonly used formula such as MDRD or CKD-EPI), or requiring chronic RRT, or died (prior to Day 60)
  - c. eGFR < 60 mL/min (at Day 90, estimated by the CKD-EPI formula based on serum creatinine), or requiring chronic RRT, hospitalized for a new episode of AKI (at Day 90), or died (prior to Day 90)
- Serology as assessed by IgG, IgE, and total immunoglobulin
- Safety parameters including (S)AEs, laboratory assessments (clinical chemistry, hematology, and urinalysis parameters not considered in the efficacy analysis), vital signs, and ECG data
- Quality of life, assessed by the EQ-5D questionnaire at baseline, ICU or intermediate care unit discharge, and Day 90
- Time from start of first administration of treatment to discharge from ICU or intermediate care unit (during the period Day 1 to Day 28, inclusive, for patients in ICU or

intermediate care unit at the start of this period) where discharge is defined as the time when the decision was made to transfer the patient (as opposed to the time of actual transfer)

- Total time in ICU or intermediate care unit from the start of first administration of study drug (during the period Day 1 to Day 90, inclusive) using the times when the decision is made to admit or discharge the patient as appropriate
- Time from start of first administration of treatment to discharge from hospital (during the period Day 1 to Day 90, inclusive) where discharge is defined as the time when the decision was made to transfer the patient (as opposed to the time of actual transfer)
- Total time in hospital from the start of first administration of study drug (during the period Day 1 to Day 90, inclusive) using the times when the decision is made to admit or discharge the patient as appropriate

## 7.4 Sample Size Calculations

A sample size of  $n_1 = 30$  patients per treatment group in Part 1 with an additional  $n_2 = 85$  patients recruited to the optimal recAP dose and placebo treatment groups in Part 2 (for a total sample size of  $n = 290$  patients) is planned. Recruitment will continue during the interim analysis so the total number of patients may exceed 290 patients. Patients recruited during this period to the dose selected in Part 2 will form part of the Part 2 populations, but those recruited to the doses that are not selected will be included in the Part 1 population. Custom programmed simulations were performed using SAS software Version 9.2 to determine power and type I error rate of the chosen sample size and design under a number of different dose response scenarios. Each scenario assumed a standard deviation of 49 mL/min for the primary endpoint ( $AUC_{1-7}$ ) with an assumed response of 60 mL/min for the placebo group, and between 60 mL/min (no treatment effect) and 79 mL/min (strong treatment effect) for the recAP dose groups.

Fifty-thousand simulations were performed to show that the 1-sided type I error rate is 2.4% (and hence is well controlled at the 1-sided 2.5% significance level). The power was defined as the probability of rejecting the null hypothesis (of no difference between treatment groups) when 1 or more recAP dose groups have an effective treatment effect, defined as a response of 69.5 mL/min. This was investigated across 7 scenarios with 10 000 simulations performed for each. In the most realistic scenarios (with strong treatment effects, i.e., responses of

79 mL/min for the medium and high recAP dose groups and a varying response of between 60 mL/min and 79 mL/min for the low-dose group) the chosen design achieved power of between 79% and 86%. This dropped to 66% to 67% for other scenarios where only the high recAP dose group had a strong treatment effect.

## 7.5 Analysis Sets

The following analysis sets will be used in the statistical analyses:

- **All enrolled set:** all patients enrolled in the study. Patients will be analyzed according to the treatment they were randomly assigned to, with a “Not randomly assigned” treatment group included if required.
- **ITT combined set:** all patients who were randomly assigned to a study drug. This is the primary analysis set for the efficacy analyses, and patients will be analyzed according to the treatment to which they were randomly assigned.
- **ITT Part 1 set:** all patients who were randomly assigned to a study drug prior to the conclusion of Part 1 of the study. This analysis set will be used to compare patients enrolled during the different parts of the study. Patients will be analyzed according to the treatment they were randomly assigned to.
- **ITT Part 1 interim set:** all patients who were randomly assigned to a study drug prior to the conclusion of Part 1 of the study and were included in the interim analysis. Patients will be analyzed according to the treatment they were randomly assigned to.
- **ITT Part 2 set:** all patients who were randomly assigned to a study drug after the conclusion of Part 1 of the study. This analysis set will be used to compare patients enrolled during the different parts of the study. Patients will be analyzed according to the treatment they were randomly assigned to.
- **Per-protocol (PP) Day 1-7 combined set:** all patients who were randomly assigned to a study drug, had no significant protocol deviations (e.g., wrong drug volume received, administration of prohibited concomitant medication, patient did not meet all inclusion criteria or met 1 or more exclusion criteria) and had complete data for the primary endpoint. The primary endpoint will be analyzed for the PP Day 1-7

combined set, with patients analyzed according to the treatment they received. See Section 10.2.2 and the Significant Protocol Deviation Rules document for further information on the handling of protocol deviations for this study.

- **Per-protocol (PP) Day 1-7 Part 2 set:** all patients who were randomly assigned to a study drug after the conclusion of Part 1 of the study, had no significant protocol deviations (e.g., wrong drug volume received, administration of prohibited concomitant medication, patient did not meet all inclusion criteria or met 1 or more exclusion criteria) and had complete data for the primary endpoint. The primary endpoint will be analyzed for the PP Day 1-7 Part 2 set, with patients analyzed according to the treatment they received. See Section 10.2.2 and the Significant Protocol Deviation Rules document for further information on the handling of protocol deviations for this study.
- **PP Day 1-28 set:** all patients who were randomly assigned to a study drug, had no significant protocol deviations (e.g., wrong drug volume received, administration of prohibited concomitant medication, patient did not meet all inclusion criteria or met 1 or more exclusion criteria) and had complete data for the key secondary endpoint. The key secondary endpoint will be analyzed for the PP Day 1-28 set, with patients analyzed according to the treatment they received. See Section 10.2.2 and the Significant Protocol Deviation Rules document for further information on the handling of protocol deviations for this study.
- **Safety set:** all patients who were randomly assigned and received a dose of study drug. All safety analyses will be based on the safety set, with patients analyzed according to the treatment they received.
- **PK set:** all patients who were randomly assigned and received at least one treatment during Part 1 of the study. The PK analyses will be based on this set, with patients analyzed according to the treatment they received.

## 7.6 Description of Subgroups to Be Analyzed

To determine whether patient groups that benefit most from recAP treatment and whether patient groups that are non-responders can be identified, additional analyses will be performed on a selection of endpoints (AUC1-7; RRT incidence from Day 1 to Day 28,

inclusive; peak value of serum creatinine from Day 1 to Day 7, inclusive; RRT-free days from Day 1 to Day 28, inclusive; time to discharge from ICU or intermediate care unit from Day 1 to Day 28, inclusive; deaths during the 90-day study period) for subgroups based on the following parameters:

- Baseline characteristics, including:
  - Kidney function markers (e.g., urine and serum creatinine, BUN/urea clearance, sodium, proteinuria, fractional excretion of sodium and urea, and urine output)
  - Tubular injury biomarkers (e.g., KIM-1, IL-18, GST-alpha)
  - Biomarkers for systemic inflammation (e.g., IL-6, CRP, LBP)
  - Glomerular filtration rate (eGFR by chronic kidney disease epidemiology collaboration [CKD-EPI])
  - APACHE II score (<25, ≥25)
- Timing from first diagnosis of SA-AKI to start of recAP treatment, e.g., in time intervals (0 to < 6 hours, 6 to < 12 hours, 12 to < 18 hours, 18 to < 24 hours).
- Baseline AKIN stage (stage 1, stage 2, stage 3)

Additional parameters may also be considered (e.g., urine output [over or under 200 mL/day], diabetes mellitus [yes or no], hypertension [yes or no], age [< 55 years old, ≥ 55 years old and < 70 years old, or ≥ 70 years old], sex (male or female), risk scores [high or low]).

Further details of these subgroups, including cut-off points and relevant outputs to be produced will be provided in the SAP.

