## **7 Statistical and Analytical Plan**

### **7.1 Primary Endpoint**

The primary endpoint will be calculated from time-corrected endogenous creatinine clearance measurements on Day 1 (first measurement after treatment) to Day 7, inclusive. Time-corrected endogenous creatinine clearance is assessed on each day during a  $6 \pm 1$  hour period and calculated in mL/min as the mean creatinine clearance over the period, which is expected to be representative of the full 24 hours for that day. The primary endpoint is the area under the time-corrected endogenous creatinine clearance curve from Day 1 to Day 7 ( $AUC_{1-7}$ ), calculated as the average of the time-corrected endogenous creatinine clearance

values over the 7 days. Specifically, denoting  $C_i$  as the mean time-corrected endogenous creatinine clearance on Day  $i$ ,  $AUC_{1-7}$  is defined as:

$$AUC_{1-7} = \frac{1}{7} \sum_{i=1}^7 C_i$$

Any missing  $C_i$  values will be handled by linear interpolation where possible, otherwise they will be imputed by last observation carried forward (LOCF). When there are no preceding post-baseline measurements to use, the baseline measurement (i.e., prior to treatment) will be carried forward.

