## 7.2 Key Secondary Endpoint

The key secondary endpoint is RRT incidence during the period Day 1 (after first treatment) to Day 28, inclusive. Should a patient die or withdraw from the study during this period without recording RRT incidence, he or she will be counted as having not required RRT. The analysis of this endpoint will be repeated excluding patients who died or withdrew from the study prior to completion of this period.

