7.2.1. Extent of Exposure

The number and percentages of patients that received any dose on Day 1, Day 2 and Day 3 will be summarized by treatment group. The number and percentages of patients will also be presented by total number of doses received (1 dose, 2 doses, 3 doses) by treatment group. All summaries will be performed using the Safety Set. The number and percentage of patients who discontinued the study prior to receiving treatment on Day 1, Day 2 and Day 3 will also be included.

Study Drug Infusion information will be presented in the form of a listing for the Safety Set, including: was patient dosed (Yes, No); infusion start time; infusion end time; route of

administration (central line, peripheral line); volume of all 4 vials drawn into the 50 mL syringe (yes, no); volume from the 4 vials discarded from the syringe based on patients weight (mL); saline added to the 50 mL syringe (mL), was total volume of 50 mL syringe administered (yes, no), and, if no, reason why total volume was not administered; and total volume of study drug administered (mL).

8. Efficacy Analysis

A hierarchical method will be employed to address any multiplicity arising from the analysis of the key secondary endpoint. In other words, the formal analysis of this endpoint will be performed only if a statistically significant result is obtained from the combination test analysis of the primary endpoint. All analyses performed on the other secondary endpoints are for exploratory purposes only; therefore, no further multiplicity adjustment is required. The results of this hierarchical method will be presented indicating where statistically significant results are obtained.

To provide an overall summary of the efficacy analyses, a table will be produced containing the results and magnitude of difference between the optimal recAP dose and placebo treatment groups for certain key endpoints. This table will be based on the ITT Combined Set.

Supportive analysis will be undertaken on a selection of endpoints (AUC_{1-7} and RRT incidence from Day 1 to Day 28, inclusive) including specific group categories as factors to assess the consistency of treatment effects.

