milestone will be patients with at least 7 days of laboratory data or who were randomized but discontinued or died prior to completing 7 days. The following outputs will be produced for these safety reviews:

Table 14.1.1.1.1	Disposition at Interim Analysis All Enrolled Set
Table 14.1.1.6.1	Concomitant Medications at Interim Analysis Safety Set
Table 14.3.1.1.1	Treatment Emergent Adverse Events at Interim Analysis by System Organ Class and Preferred Term Safety Set
Table 14.3.1.1.2*	Serious Treatment Emergent Adverse Events at Interim Analysis by System Organ Class and Preferred Term Safety Set
Table 14.3.1.3.1	Treatment Emergent Adverse Events at Interim Analysis by Relationship to Study Drug Safety Set
Table 14.3.2.1*	Summary of Cause of Death at Interim Analysis by System Organ Class and Preferred Term Safety Set
Table 14.3.5.3.1	Hematology Shift Table by Treatment at Interim Analysis Safety Set
Table 14.3.5.3.2	Laboratory Results: Hematology at Interim Analysis Safety Set
Table 14.3.5.4.1	Clinical Chemistry Shift Table by Treatment at Interim Analysis Safety Set
Table 14.3.5.4.2	Laboratory Results: Clinical Chemistry at Interim Analysis Safety Set
Table 14.3.6.2.1	Change from Baseline in Vital Signs at Interim Analysis Safety Set
Figure 14.3.6.2.1	Time-course plot of Vital Signs at Interim Analysis Safety Set
Table 14.3.7.1.1*	APACHE II Score at Interim Analysis Safety Set
Listing 16.3.1.1.2*	Deaths Safety Set

* Outputs were requested after the first DMC meeting.

References to ‘Interim Analysis’ will be removed from all titles and footnotes when outputs are provided at safety reviews.

Additional electronic reviews of AE listings provided by pharmacovigilance (PVG) will be conducted at planned time points and the DMC can request ad hoc reviews. See [Table 15-2](#) for a full summary of the planned reviews.

12. Changes in the Planned Analysis

As part of the primary efficacy analysis an additional analysis set PP Day 1-7 Part 1 has been added. The protocol states that primary endpoint should be carried out separately for Part 1 and Part 2, however to do this analysis on the PP Set, the PP Day 1-7 Part 1 Set is needed to be defined to obtain the analysis for Part 1 of the study.

The following are changes from the Protocol Amendment v2.0:

Table 12-1 Summary of Changes from Planned Analysis and Reason

Change	Change
List of subgroups (Sections 2.3 and 8)	Microbial Infection added

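### The SAP runs subgroup analyses on two of the protocol's six endpoints without declaring the cut, so no planned subgroup table would show deaths behind a lower RRT rate

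*Protocol*

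**What the plan says.** Protocol 7.6 states that subgroup analyses will be done on a named set of endpoints. After AUC1-7 and RRT incidence it lists "peak value of serum creatinine from Day 1 to Day 7, inclusive; RRT-free days from Day 1 to Day 28, inclusive", then time to ICU or intermediate care discharge up to Day 28, and last "deaths during the 90-day study period) for subgroups based on the following parameters". It closes with a delegation: "Further details of these subgroups, including cut-off points and relevant outputs to be produced will be provided in the SAP".

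The opening of SAP Section 8 confines the supportive analysis to AUC1-7 "and RRT incidence from Day 1 to Day 28, inclusive) including specific group categories as factors". Sections 8.1.1 and 8.1.5 carry this out for AUC1-7, and 8.2.1 extends it to RRT incidence. SAP 2.3 keeps the objective of finding patients who benefit most and patients who do not respond.

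On declared changes, the Table 12-1 row beginning "List of subgroups (Sections 2.3 and 8" records only that microbial infection was added. In Section 13, the entries on subgroups say that the group categories enter the models as factors or covariates. No entry mentions a removed endpoint.

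On death, a patient who dies or withdraws by Day 28 without recorded RRT is treated as follows: "he or she will be counted as having not required RRT" (Protocol 7.2, repeated in SAP 8.2.1). AUC1-7 has no rule for death. In Protocol 7.1, missing daily clearance "values will be handled by linear interpolation where possible, otherwise they will be imputed by last observation carried forward (LOCF", and SAP 8.1 does the same.

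**The concern.** The protocol promises a subgroup view of mortality and the SAP does not deliver one. The two endpoints it keeps do not fill the gap. If recAP increased early death in some subgroup, fewer of those patients would live long enough to start RRT. The scored RRT rate there would fall and look like benefit.

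This matters because a primary objective is to support the Phase 3 programme, and RRT incidence is described as a relevant Phase 3 endpoint. A subgroup could be carried forward on a lower RRT rate while its deaths were never tabulated. Death is not rare in this population: both documents cite mortality of up to 70% in SA-AKI.

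**Working it through.** **1. Endpoint by endpoint.**

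| Named in Protocol 7.6 | By-factor analysis in the SAP | Whole-trial analysis in the SAP |
|---|---|---|
| AUC1-7 | 8.1.1, 8.1.5 | 8.1.1 |
| RRT incidence, Day 1-28 | 8.2.1 | 8.2.1 |
| Peak serum creatinine, Day 1-7 | none | 8.2.2.1 |
| RRT-free days, Day 1-28 | none | 8.2.2.1 |
| Time to ICU discharge, Day 1-28 | none | 8.3 |
| Deaths over 90 days | none | 8.2.2.2, 9.1.6 |

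Six are named, two kept and four dropped. RRT-or-death (SAP 8.3, first composite) also has no by-factor version. The repeat analyses that address death remove the patients who died (8.1.4 before Day 8; 8.2.1 before completing 28 days), and neither is specified by subgroup. The factors enter the models with no stated treatment-by-factor interaction, so any difference between subgroups would be seen mainly in the descriptive by-factor summaries.

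**2. How AUC1-7 treats death.** Carrying the last value forward:
- Clearances of 20 then 60, death after Day 2: (20 + 6 × 60)/7 = 54.3. A survivor who stays at 60 also scores 54.3.
- Clearances of 20 then 10, death after Day 2: (20 + 6 × 10)/7 = 11.4, well below the planning mean of 60 for placebo.

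Death itself adds no penalty, but decline before death still lowers the score.

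**3. How RRT incidence treats death.** The documents give no planning rates for RRT or death, so all of these are assumptions. Take constant hazards over 28 days and no recAP effect on the kidney. Let H_R = −ln(1 − 0.40) = 0.5108 and, on placebo, H_D = −ln(1 − d) for death before RRT, doubled on recAP.

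- RRT incidence = H_R/(H_R + H_D) × [1 − exp(−(H_R + H_D))]
- Death before RRT = H_D/(H_R + H_D) × the same bracket
- RRT or death = the bracket itself

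For d = 15%:
- Placebo: 0.5108/0.6733 × (1 − 0.6 × 0.85) = 0.7586 × 0.49 = 37.2%.
- recAP: 0.5108/0.8359 × (1 − 0.6 × 0.7225) = 0.6111 × 0.5665 = 34.6%.

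| d | RRT incidence, placebo → recAP | Death before RRT | RRT or death |
|---|---|---|---|
| 10% | 38.1% → 36.4% | 7.9% → 15.0% | 46.0% → 51.4% |
| 15% | 37.2% → 34.6% | 11.8% → 22.0% | 49.0% → 56.7% |
| 20% | 36.2% → 32.9% | 15.8% → 28.7% | 52.0% → 61.6% |

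A simpler model agrees in direction. Suppose 40% of patients who do not die early receive RRT, and early death is 5% on placebo and 15% on recAP. Scored RRT is 0.95 × 0.40 = 38% against 0.85 × 0.40 = 34% (odds ratio 0.84). RRT-or-death is 43% against 49% (odds ratio 1.27). With RRT rates of 30% to 50%, and early death of 10% to 20% on recAP against 5% on placebo, the RRT odds ratio runs from 0.74 to 0.93 and the composite from 1.11 to 1.56.

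**4. What a subgroup can show.** The planned sizes give 30 + 85 = 115 per arm for the selected dose and placebo, so a quartile has 115/4 ≈ 29 per arm.
- RRT at 37.2% against 34.6%: the 95% half-width is 1.96 × √[(0.372 × 0.628 + 0.346 × 0.654)/28.75] ≈ 25 points.
- Deaths before RRT at 11.8% against 22.0%: about 3 patients against 6.
- Power for 90-day death at two-sided 5%, for assumed rates of 30% against 15%, 30% against 20% and 25% against 15%: 27%, 14% and 15% in a quartile; 49%, 23% and 27% in a half-sample.

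**The case against.** The protocol hands the choice of relevant outputs to the SAP, so the SAP had room to decide what to print. The change of method was also logged in Section 13. This narrows the point but does not remove it. Choosing outputs covers how named endpoints are presented. It does not plainly cover dropping four of six without record, when Table 12-1 finds room for additions as small as kidney function at Days 14 and 21.

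Death is not neglected at trial level. SAP 8.2.2.2 gives counts, percentages and CMH tests at Day 28 and Day 90, 8.3 analyses RRT-or-death, 9.1.6 tabulates causes and lists all deaths, and Section 11 sends death outputs to the DMC. That stands: only the subgroup view is missing.

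Subgroup death counts would also be noisy. The 13 factors in 8.1.5 have 48 categories, so chance imbalances are likely. This stands too. It argues against testing and for plain counts.

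A reader might go further and infer that neither retained endpoint can reflect harm that ends in death. For AUC1-7 the documents do not support that, because a patient who deteriorates before dying keeps a low value.

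**Conclusion.** The departure is real and undeclared: four of the six subgroup endpoints in Protocol 7.6 have no by-factor analysis in the SAP, and Sections 12 and 13 do not say so. The consequence is clearest for RRT incidence, which credits death without RRT. AUC1-7 is only silent about death as such.

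Under the assumed rates, a doubled hazard of death before RRT produces a spurious fall in RRT of 1.7 to 3.3 points, while RRT-or-death rises by 5.4 to 9.6 points. The direction follows from the scoring rule; the size rests on the assumed 40% RRT rate, the 10% to 20% range for death, the doubling, and independent hazards. In a quartile subgroup a shift of that size is well inside sampling error.

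The practical weight is therefore moderate. Sample size, alpha and the confirmatory test are untouched, and all subgroup work is exploratory. Two stronger inferences are not supported: that mortality was removed from the plan, since it is analysed overall, and that the cut was made to hide harm, since the documents give no reason for it at all.

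**What to change.** In SAP 8.1.5, add to the by-factor summaries the number and percentage of deaths by Day 90, by arm (selected dose and placebo), for each of the 13 factors. Preferably add RRT-or-death by Day 28 beside them, so that a lower RRT rate can be read with its deaths. State that these are descriptive and that no tests will be done.

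For peak creatinine, RRT-free days and time to ICU discharge, either restore them as by-factor summaries or add a row to Table 12-1 recording their removal and the reason.

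The cost is SAP wording and one table per factor for deaths, from data already collected. Adding the composite doubles that. Restoring the other three endpoints would mean up to 3 × 13 = 39 further tables; declaring their removal costs a few lines. Formal error control is unaffected, but many cells will be small, and the text should warn against reading isolated imbalances as findings.
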